## **8.3 QUALITY OF LIFE PATIENT QUESTIONNAIRES**

All study participants will be administered three questionnaires: FACT-P, AUA SS, and SHIM. The questionnaires will be used to assess the impact of therapy on the patient's perception of their quality of life the intervals as indicated within the study calendar. Questionnaires may be mailed to the subject in pre-metered envelope if they are unable to come into the clinic to complete them (ie: due to COVID19 travel restrictions). The subject will complete the questionnaires at home and then mail the completed questionnaires back to the main site in the provided envelope.

## **8.4 SUB-STUDY SOCIAL DETERMINANTS SURVEY:**

For patients who consent to the main study, SES, social factors, behavioral factors, shared decision-making, knowledge and perceptions of precision medicine, and perceived stress measurements will be obtained by self-report. Patients will have the option to be administered the survey over the telephone, or they can complete the survey during their clinic visit of the first vaccine treatment. This survey will provide a numeric readout. Investigators will measure chronic SES stressors in terms of income, employment status, and financial strain. The Life Events Questionnaire (LEQ; (116)) is a validated measure that captures life events across multiples areas. The Health, Work (e.g., difficulty finding a job); Residence (e.g., difficulty finding housing), and Financial subscales of the LEQ will be used for the purposes of the current study. In addition, the validated Perceived Stress Scale (117) and the Everyday Discrimination Scale ((118)) will be used to capture perceived stress and discriminatory stress, respectively.

Investigators will use the short form of the Loneliness Scale (119) and Interpersonal Support Evaluation List (ISEL; (120)) to measure social isolation and support, respectively. Financial strain will be measured by a validated Likert-style item that asks participants if they have some, just enough, or not enough money left over at the end of the month. Cancer-related stressors will

be measured in terms of perceived stress about being diagnosed with prostate cancer and clinical stressors) and perceived risk and control about prostate cancer recurrence. Perceived risk and control will be measured using items from previous research on cancer recurrence among breast cancer survivors ((121)). Items relating to knowledge and perceptions of precision medicine were adapted from previous research on genetically targeted care (123). Health behavior items measuring moderate exercise and diet behaviors were taken from the validated NCI-HINTS (124). Investigators will also measure clinical stressors in terms of stage and grade of prostate cancer diagnosis and the presence of surgery-related side effects. Clinical stressors will be abstracted from medical records.

## 8.5 OPTIONAL SUB-STUDY TRIER SOCIAL STRESS TEST

For patients who consent to the optional sub-study, the TSST ((103)) will be used to induce and measure a stress response. The TSST is a standardized psychological stress challenge which has been used extensively in research studies. A meta-analysis supports that it is the gold standard for evoking an HPA axis stress response in a laboratory setting ((104)). The ACTH and cortisol changes induced by the TSST reflect the sequence of HPA axis activity. That is, ACTH peaks first, at the end of the 10-minute stressor, and returns to baseline level within 40 minutes. Total plasma cortisol peaks 20 minutes after ACTH, and returns to baseline about an hour after initiation of the stressor. The TSST will be administered at the South Carolina Clinical and Translational Research Institute (SCTR) at MUSC.

Effort will be made to ensure that the experimental procedures and assessments for the TSST are collected at the same time point for each participant to control for changes in cortisol levels due to time of day (diurnal patterns). However, should a time variation occur, this will be considered a deviation, and patients will have to be rescheduled for their TSST. A time lapse of no more than 15 minutes will be permissible for conducting the TSST. The times of procedures will be collected within the source worksheets and any time delays will be recorded.

Because of the logistics for scheduling and the TSST assessment, the timeframe for conducting the assessment may be prior to the main study registration. The TSST must be administered after the patient provides consent to the optional sub-study and any time before the patient begins PROSTVAC treatment. The TSST experimental stress challenge should begin at 4:00 pm. During the TSST, participants are told at 4:00 pm that he will soon perform to an audience which includes a speech and arithmetic task. The topic of the speech is why he should be hired for a particular job (the individual's "dream job"). The participant will deliver the speech as though speaking to a group of hiring managers. The experimenter then tells the participant that he has five minutes to prepare the speech, and starts the countdown clock (which is placed in view of the individual). The experimenter leaves the room to allow the participant to prepare. At 4:33 pm, the participant is escorted by the experimenter to an interview room, where three individuals unfamiliar to the participant (the audience) are seated; the individual is instructed by one audience member (the spokesperson) to stand and begin his prepared speech (without notes).

The speech is delivered for five minutes. At the end of the speech task (4:44 pm), the individual is instructed to serially subtract 13 from 1,022 as quickly and accurately as possible. If the

participant makes a mistake, he is told to begin again at 1,022. The mental math recitation continues for five minutes, at the end of which time, the spokesperson instructs the individual to stop. The experimenter enters the room and escorts the participant back to the initial room. The TSST, in total, spans 10 minutes. The first post-stressor assessment occurs immediately following the task (or control condition) at 4:46 p.m. and the last post-stressor assessment occurs at 5:10 p.m.

Investigators will measure stress reactivity using saliva samples that are collected prospectively during the TSST (see Figure 3). The change in cortisol level may be expressed in several ways, such as change from pretest to maximum increase, area-under-the-curve, or an index incorporating multiple values. If needed, heart rate, BP can similarly quantified. Data on cortisol, heart rate, blood pressure will be used to generate allostatic load during an acute stress response. An 11-point scale (0-10) will be used for the Subjective Units of Distress variable (SUD). Investigators will also measure heart rate variability (HRV) and blood pressure using standard medical equipment and procedures during the TSST.

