## 8.6 ALLOSTATIC LOAD

Allostatic load will be determined based on laboratory results and clinical measures that will

Figure 3. TSST Procedures and Timeline		
TIME	EXPERIMENTAL PROCEDURE	STRESS ASSESSMENT
4:00-4:15pm	Acclimation period (15 minute duration)	Patient arrives and given relaxation tools (i.e. spa video, magazine, nature scenes)
4:16 Baseline (immediately following acclimation period)	Laboratory Stress measurements	Take cortisol, BP, HR, and assess SUD
4:28pm Immediately before TSST (12 minutes following baseline)	Laboratory Stress measurements	Take cortisol, BP, HR, assess SUD, and explain the task and give participant paper to write notes
4:33- 4:44pm (5 minutes following 2 nd lab measurements)	TSST	
5 minutes	Interview task	
5 minutes	Arithmetic task	
Post TSST stress assessments (12 minute increments)		
4:46pm Post TSST (2 minutes following TSST)	Post-TSST Assessment	Cortisol, BP, HR, SUD
4:58pm 12 mins post TSST	Post-TSST Assessment	Cortisol, BP, HR, SUD
5:10pm 24 mins post TSST	Final Post-TSST Assessment	Cortisol, BP, HR, SUD
Note: Patients more than 15 minutes late are unable to participate in the TSST and would need to be rescheduled.		

include the following; blood pressure, heart rate, total cholesterol, HDL cholesterol, body mass

index (BMI), C-reactive protein (CRP), DHEAS and interleukin-6 (IL-6). Cortisol will also be measured for those participating in the optional sub-study. We will use established methods to determine allostatic load. These methods use established clinical cutoffs to categorize biomarkers as being within normal ranges. For instance, a systolic blood pressure  $\geq 140$  mm/Hg and CRP  $\geq 3$  mg/L are values that are outside of normal ranges. The values for each biomarker will be coded into a dichotomous variable (1=above normal cutoff and 0=below normal cutoff). Scores for allostatic load will be calculated by summing dichotomous values for each biomarker.

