### **10.3 SOCIOBIOLOGICAL RESPONSE TO STRESS OPTIONAL SUB-STUDY OBJECTIVES**

The investigators expect around 70-80% of patients will consent for the sub-study, which leads to the sample size around 30-40 patients for the analysis. Through this sub-study, the investigators will explore the relation between stress responses and clinical outcomes for the entire patient population and for racial subgroups. The following statistical plan will be used.

Aim 1: To evaluate the effects of stress reactivity on the development of an effective anti-tumor immune response in this patient population.

We will perform the following analyses to better understand how stress reactivity affects the anti-tumor immune response: 1) correlation analysis between the anti-tumor immune response and stress reactivity measures; 2) logistic regression in which we will regress the anti-tumor immune response of each patient on stress reactivity adjusting for covariates (e.g. age, perceived stress).

Aim 2: To evaluate the difference in terms of stress reactivity based on SES, perceptions of social stressors, and AL between racial subgroups.

Descriptive statistics of stress reactivity measures will be summarized for the entire patient population and for each racial group. Wilcoxon rank sum test or a Fisher's exact test will be used to explore the potential statistical significance among those measures (e.g. SR, clinical history, psychosocial factors (e.g., life stress events, social isolation), and genetic variants in the GR receptor gene) between racial subgroups. In addition, a discriminant analysis (e.g. quadratic discriminant analysis or nearest neighbor approach) for the entire patient population and for each racial group will be used to classify patients as high or low stress responders based on changes in cortisol during the TSST. Cross validation will be used to exam the misclassification rates.

Aim 3: To evaluate the difference between racial subgroups for the magnitude and distribution of stress responses with biological (AL) and immunologic measure of vaccine effect.

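### Section 8.5 and Figure 3 give incompatible stress-test schedules (task disclosed at 4:00 pm versus the 4:28 step), and the Section 8.5 clock times contradict their own durations

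*Combined protocol and SAP*

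**What the plan says.** Section 8.5 sets the start of the session: "The TSST experimental stress challenge should begin at 4:00 pm". It continues: "During the TSST, participants are told at 4:00 pm that he will soon perform to an audience which includes a speech and arithmetic task". Preparation comes next, with no clock time: "The experimenter then tells the participant that he has five minutes to prepare the speech, and starts the countdown clock". The participant is taken to the interview room at 4:33 and speaks for five minutes. The text then says: "At the end of the speech task (4:44 pm), the individual is instructed to serially subtract". The arithmetic lasts five minutes, the whole test is said to last 10 minutes, and the first post-stressor assessment is placed directly after the task, at 4:46.

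Figure 3 (printed in Section 8.6) gives another sequence. The first 15 minutes are acclimation with relaxation material. The next entry is "4:16 Baseline (immediately following acclimation period"). The 4:28 entry reads: "Take cortisol, BP, HR, assess SUD, and explain the task". The test itself occupies 4:33 to 4:44, with samples at 4:46, 4:58 and 5:10.

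The last paragraph of Section 8.5 refers to Figure 3 for the saliva samples. It allows reactivity to be expressed as pretest-to-maximum change, as area under the curve (AUC), or as an index of several values. It does not say which of the two pre-test samples is the pretest value.

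**The concern.** A laboratory stress test needs a reference sample taken before the participant knows what is coming. Under the Section 8.5 script he knows from 4:00, so neither pre-test sample meets that condition. Under Figure 3 the 4:16 sample does, and so does the 4:28 sample if the steps in that row are done in the order listed. If some sessions follow the text and others the figure, the reactivity values are not comparable between men.

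Reactivity enters all three sub-study aims in Section 10.3. It is the explanatory variable for immune response in Aim 1. In Aim 2 it is used to "classify patients as high or low stress responders based on changes in cortisol during the TSST". In Aim 3 it is a covariate in the mixed model for allostatic load. Section 2.6.2 also wants the observed range of stress responses for planning larger studies, so a distorted range would carry forward.

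The protocol itself treats timing here as important. Section 8.5 makes a departure in time of day a deviation that requires rescheduling. It also requires the test before the first PROSTVAC dose, so a session run on the wrong script cannot be repeated once treatment has begun.

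**Working it through.** This is clock arithmetic on times and durations in Section 8.5 and Figure 3.

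**1. Disclosure relative to the pre-test samples**

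| | Section 8.5 text | Figure 3 |
|---|---|---|
| 4:00 to 4:15 | challenge begins, task announced | relaxation only |
| Task disclosed | 4:00 | 4:28 step, listed after the measurements |
| 4:16 sample | 4:16 − 4:00 = 16 min after disclosure | 4:28 − 4:16 = 12 min before disclosure |
| 4:28 sample | 4:28 − 4:00 = 28 min after disclosure | immediately before disclosure, if the listed order is kept |

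The text has no pre-test sample times of its own. The two samples in the middle column come from Figure 3, the schedule that Section 8.5 cites.

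The text also fits poorly with itself on preparation. If the five minutes start at about 4:00, they end at about 4:05, which leaves 4:33 − 4:05 = 28 minutes unaccounted for. Five minutes counted back from 4:33 gives 4:28, the time in Figure 3.

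**2. Task times within the Section 8.5 text**

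The stated figures are a 10-minute total and a 4:46 sample after the task.

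- By clock times: the speech starts at 4:33 and is said to end at 4:44. Arithmetic then runs to 4:44 + 5 = 4:49. The total is 4:49 − 4:33 = 16 minutes, and the 4:46 sample falls 3 minutes before the end. Neither stated figure is reproduced.
- By durations: 4:33 + 5 = 4:38 for the end of the speech, and 4:38 + 5 = 4:43 for the end of the arithmetic. The total is 10 minutes, and 4:46 falls 3 minutes after the end. Both stated figures are reproduced, but the stated 4:44 end of speech is then wrong by 4:44 − 4:38 = 6 minutes.
- By Figure 3: the test ends at 4:44, and the 4:46 sample is 2 minutes later.

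The 4:44 in the text equals the end of the whole test in Figure 3, so it looks like a misplaced time.

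**3. Direction of a possible bias**

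Let B be the undisturbed pretest cortisol, M the maximum after the test, and d the rise already present at the pretest sample because of anticipation. The intended change is M − B. The measured change is M − (B + d) = (M − B) − d. If M is unaffected, the proportion lost is d / (M − B). The documents give no value for d, so the loss may be anything from zero upwards. If anticipation also raises M, the loss is smaller. For AUC the direction depends on whether the baseline is subtracted, which the plan does not say.

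**4. Effect of the possible arithmetic overrun**

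Section 8.5 places the ACTH peak at the end of the stressor and the plasma cortisol peak 20 minutes after that. Test ends of 4:43, 4:44 and 4:49 give cortisol peaks at 5:03, 5:04 and 5:09. All come before the last sample at 5:10. The overrun reading therefore changes what the 4:46 sample represents, but it does not touch the baseline or push the expected peak past the sampling window.

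**The case against.** The strongest reply is that Figure 3 governs. Section 8.5 cites it for saliva sampling, and a team that works from it throughout takes the 4:16 baseline before any disclosure. The 4:00 in the text may simply mark the start of the session, since the narrative goes from announcement to five minutes of preparation to entry at 4:33, which fits a 4:28 announcement. On this view the matter is a drafting slip.

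Much of this stands. A reader might infer from the text that reactivity is measured from a stressed baseline. The documents do not support that as a statement of fact, because it holds only for sessions run on the Section 8.5 script. A reader might also infer that the 4:46 sample certainly falls inside the arithmetic. That is one of two readings, and the text's own durations give the other. Even on the first reading a post-task sample is affected, so it adds nothing to the baseline argument.

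What does not stand is that the cross-reference settles the matter. It fixes when saliva is collected. It does not cancel an explicit instruction about what the participant is told and when. Because the text has no pre-test samples of its own, a team that uses its script would naturally take the sample times from Figure 3, and that is the combination that causes the problem. Section 8.5 already has procedure times recorded on source worksheets, which would help to detect the problem afterwards but would not prevent it.

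**Conclusion.** The two schedules conflict on disclosure (4:00 against the 4:28 step), and the Section 8.5 clock times conflict with its durations (16 minutes against 10, and an end at 4:49 against a sample at 4:46). Both follow directly from the page and need no assumption.

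The consequence is conditional. If the Section 8.5 script is followed, both pre-test samples come after disclosure, by 16 and 28 minutes. If anticipation raises cortisol by then, pretest-to-maximum change is understated. No percentage can be attached, because the documents contain no anticipatory cortisol figure, and the kinetics in Section 8.5 describe plasma cortisol after the full test, not saliva after an announcement. A reader might go on to infer that true high responders will be classed as low. That is possible, but nothing in the documents shows it.

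The scope is limited to the optional sub-study, whose analyses Section 10.3 describes as exploratory. The primary relapse-free survival endpoint and safety monitoring are unaffected. The correction is still worth making, because this is an operating procedure, it feeds all three sub-study aims, and a session cannot be repeated after treatment starts.

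**What to change.** Align the Section 8.5 script with Figure 3:

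- Delete the 4:00 pm disclosure. Use 4:00 to 4:15 for acclimation only, and take the baseline sample at 4:16.
- State that nothing about the task is disclosed until the 4:28 sample and measurements are complete. Then explain the task and allow five minutes' preparation.
- Delete 4:44 as the end of the speech. Place a five-minute speech and a five-minute arithmetic task within the 4:33 to 4:44 block, with the first post-task sample at 4:46.
- Name the 4:16 sample as the pretest reference for change and for AUC.
- Enter the actual time of disclosure among the procedure times already kept on the source worksheets.

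While editing, correct the Figure 3 labels for 4:58 and 5:10. They are given as 12 and 24 minutes after the test, but those intervals run from the 4:46 sample. From the 4:44 end they are 14 and 26 minutes.

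The cost is wording in the protocol, the session script and the worksheet. No sample, visit or staff is added. If sessions have already been run, record which script each one followed, so that the reactivity analyses can take it into account.

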Descriptive statistics will be summarized for the AL measurements (e.g. median) at each time point (baseline, day 85, day 225, and day 730 or off study) for the entire patient population and for each racial group. We will compare the mean difference between two consecutive time points between two racial groups using a Wilcoxon rank sum test. A linear mixed model will also be fitted in which we will regress AL measurements on racial group, time, stress reactivity (may consider interaction terms) to explore the AL response profile difference. The outcome of RFS will be evaluated using Kaplan-Meier estimates and the statistical significance of difference in RFS between racial groups will be tested by a logrank test. In addition, a cox regression model will be explored.

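### Stress-test cortisol can count toward baseline allostatic load, which Aim 3 then regresses on stress reactivity defined by the same cortisol

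*Combined protocol and SAP*

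**What the plan says.** - **Stress reactivity (Section 8.5).** "Investigators will measure stress reactivity using saliva samples that are collected prospectively during the TSST". The index is left open: a rise from the pre-test value to the maximum, an area under the curve, or a composite of several values. Heart rate and blood pressure are secondary: "If needed, heart rate, BP can similarly quantified".
- **Allostatic load (Sections 8.5 and 8.6).** Section 8.5 states: "Data on cortisol, heart rate, blood pressure will be used to generate allostatic load during an acute stress response". Section 8.6 lists eight biomarkers (blood pressure, heart rate, total and HDL cholesterol, BMI, CRP, DHEAS, IL-6) and adds: "Cortisol will also be measured for those participating in the optional sub-study". Each biomarker becomes 0 or 1 against a clinical cutoff, and "Scores for allostatic load will be calculated by summing dichotomous values for each biomarker". Section 8.6 does not say whether cortisol is scored, or from which sample.
- **Analysis (Section 10.3, Aim 3).** AL is summarised at baseline, day 85, day 225 and day 730 or off study. Differences between consecutive time points are compared. In a linear mixed model, "we will regress AL measurements on racial group, time, stress reactivity", with interaction terms as an option.
- **Timing (Section 8.5, Appendix A).** The TSST is given once, before the first vaccine dose.

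**The concern.** If TSST cortisol is an AL item, part of the outcome in the Aim 3 model is built from the measurement that defines the regressor. A test of no association then has the wrong null value, because some correlation is present even when chronic load and acute reactivity are unrelated. Its sign depends on choices the plan leaves open. Scoring a high pre-test cortisol adds a point to AL and lowers peak-minus-pre reactivity. Scoring a high peak adds a point and raises it.

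There is a second effect. Sub-study men would have a cortisol item at baseline that they cannot have later, and that other men never have. AL would then not be one scale across visits or across men.

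What is at stake is the reading of one exploratory aim. Section 2.6 presents AL as central to the sub-study and intends its data for planning larger studies, so a built-in correlation could be carried forward.

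**Working it through.** The plan gives no effect size, alpha or power for AL against reactivity, so there is no figure to reproduce. The check is whether the overlap exists, and then how large it would be.

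**Does the overlap exist?** The only cortisol collection the protocol schedules is the TSST saliva series (Section 8.6, Figure 3). Cortisol is not in the clinical laboratory list of Section 7.1 or among the research blood assays of Section 8.1. If cortisol is scored in AL, it is therefore TSST cortisol, and only at baseline.

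**Assumptions (not in the documents).** Each item is above its cutoff with p = 0.3. Pre-test and peak cortisol have equal variance and correlation ρ = 0.5-0.8. The other eight items are independent of cortisol and of each other, and each correlates ω = 0.5-0.8 with itself between visits. All eight are treated as available at every visit, a simplification because Section 7.1 schedules the lipid panel at baseline only. Pre-test cortisol is scored. Tests are two-sided at 5%. n = 24-30: Section 10.3 states 30-40 men, but its 70-80% uptake applied to the 33 enrolled in Section 10.1 gives 23-26.

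**Step 1, cortisol item against pre-test cortisol.** The correlation is φ(0.524)/√(0.3 × 0.7) = 0.348/0.458 = 0.759.

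**Step 2, pre-test cortisol against reactivity.**
- Peak minus pre: −√((1−ρ)/2) = −0.500 (ρ = 0.5) or −0.316 (ρ = 0.8).
- Area-type index (pre plus peak as proxy): √((1+ρ)/2) = 0.866 or 0.949.

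**Step 3, baseline AL.** One of nine equal, independent items correlates 1/√9 = 0.333 with the sum. So r = 0.759 × 0.333 × (Step 2):
- peak minus pre: −0.126 or −0.080;
- area type: 0.219 or 0.240.

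**Step 4, rejection rate.** Φ(−1.96 + |atanh r|√(n−3)) + Φ(−1.96 − |atanh r|√(n−3)).
- Peak minus pre: 6.6% (r = 0.080, n = 24) to 10.1% (r = 0.126, n = 30).
- Area type: 17.5% (r = 0.219, n = 24) to 24.6% (r = 0.240, n = 30).

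Simulation under the same kind of assumptions gave 6-11% and 17-26%. Scoring the peak instead reverses the sign for peak minus pre, with similar size.

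**Step 5, average over four visits.** The covariance is divided by four: 0.348 × (Step 2)/4. The variance of the mean is 8 × 0.21 × (1 + 3ω)/4 + 0.21/16, which is 1.063 at ω = 0.5 and 1.441 at ω = 0.8.
- Peak minus pre: |r| from 0.0275/1.200 = 0.023 to 0.0435/1.031 = 0.042.
- Area type: r from 0.0753/1.200 = 0.063 to 0.0826/1.031 = 0.080.
- Rejection runs from 5.1% (r = 0.023, n = 24) to 7.0% (r = 0.080, n = 30). Simulation gave 5-7%.

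**Step 6, reactivity by time.** Baseline minus one later visit has variance 0.21 + 2 × 1.68 × (1−ω). At ω = 0.5 this is 1.89, the same as the nine-item baseline score (9 × 0.21), so the Step 3 and 4 results carry over. More stable items, or comparison with the average of later visits, leave less noise and raise the rate. Simulation gave 7-12% for peak minus pre and 22-32% for area type.

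**Step 7, unequal scale.** Expected baseline AL is 9 × 0.3 = 2.7 with cortisol and 8 × 0.3 = 2.4 without. A sub-study man's AL would fall by 0.3 on average after baseline by construction.

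**Step 8, cortisol removed.** The induced covariance is zero. Simulated rejection was 5.2% at n = 30.

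**The case against.** The strongest reply is that the plan may mean two different scores. Section 8.5 speaks of load during an acute stress response. Section 8.6 describes a score from laboratory and clinical measures and says only that cortisol will be measured, not that it is scored. This stands as far as it goes: the overlap is permitted by the text, not spelled out. But the plan never separates the two scores, Aim 3 says only AL, and Section 8.6 mentions cortisol inside the AL definition.

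A second reply is that the planned model uses four visits and the TSST touches one. That also stands. The main effect of reactivity averaged over visits is close to nominal. It does not cover a baseline analysis or a reactivity-by-time term, which Section 10.3 allows.

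Some stronger readings are tempting, and the documents do not support them:
- **A three-item acute score (cortisol, heart rate, blood pressure) as the Aim 3 outcome.** No analysis in Section 10.3 names it, and it could not be repeated at days 85, 225 and 730.
- **Blood pressure and heart rate in the Section 8.6 score taken from the TSST.** Section 8.6 does not say so. They overlap with reactivity only if taken from the TSST session and also used as optional reactivity measures.
- **A contaminated test in Aim 2.** The aim reads "To evaluate the difference in terms of stress reactivity based on SES, perceptions of social stressors, and AL between racial subgroups", but its methods compare measures between racial groups and classify responders by cortisol change. They specify no test of AL against reactivity.
- **Spurious racial differences.** If cortisol is distributed alike in both groups, the artefact is the same in both. No calculation here shows otherwise.

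**Conclusion.** The point holds in limited form. As written, TSST cortisol can enter baseline AL, and Aim 3 relates AL to reactivity measured by the same cortisol. The visit-averaged effect is barely disturbed (about 5-7% against 5%). Baseline and reactivity-by-time associations are more exposed: about 6-12% with peak minus pre and 17-32% with an area-type index. The choice of index, which the plan leaves open, matters most.

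These rates are illustrative. They depend on the assumed prevalence, pre/peak correlation, item stability and sample size, and on cortisol being scored at all. If it is not scored, this artefact disappears.

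The sub-study is optional and exploratory, and the primary endpoint and its decision rule are untouched. The change is still worth making because it settles an ambiguity and removes an avoidable correlation.

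**What to change.** In Sections 8.5, 8.6 and 10.3, state that:

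- the AL score used in Aim 3, and in any other analysis with stress reactivity, excludes cortisol and takes blood pressure and heart rate from the clinic visit, not the TSST session;
- this definition is the same for all men, in or out of the sub-study;
- the acute TSST composite may be reported descriptively but is not related to stress reactivity.

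This needs wording only and no new measurements. The small downside is that cortisol is no longer an AL item in these exploratory analyses. The change does not by itself make the score identical at every visit: Section 7.1 schedules the lipid panel at baseline only, so Section 8.6 should also say how the two cholesterol items are handled later.
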